4.3.3 Exploratory outcomes statistical models

4.3.3.1 TNF α

Individual LPS-stimulated WB TNF α levels (pg/mL), will be listed and summarised by treatment, study day and time point using descriptive statistics (n, arithmetic mean, SD, geometric mean, geometric SD, geometric CV%, minimum, median, and maximum).

Arithmetic mean (+/- SE bars) TNF α levels versus time will be plotted by study day and treatment. A panel plot will be used with Day 1 and Day 15 displayed side-by-side. In addition, a graphical presentation of individual LPS-stimulated WB TNF α levels (pg/mL) following AZD9567 treatment versus individual AZD9567 levels (nmol/L) from the same sampling time points will be made, which will include a plot of all timepoints on the final page. For this figure, AZD9567 levels with non-quantifiable results will be displayed as the lower limit of quantification.

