1.2 Rationale for study design, doses and control groups

This is a Phase 2a, randomised, double-blind, parallel arm study to assess the efficacy, safety and tolerability of 40 mg AZD9567 compared to prednisolone 20 mg in patients with active RA. According to the American College of Rheumatology Guidelines, short-term glucocorticoid treatment is indicated to control disease in RA patients with moderate to high disease activity. The current study randomizes eligible patients with established RA and

moderate to high disease activity as defined by ACR Guidelines (DAS28>3.2) to prednisolone 20 mg or AZD9567 40 mg for 14 days.

Prednisolone 20 mg is chosen as a moderate dose of prednisolone that falls within the ACR recommendations for treatment of active disease as moderate doses have been shown to be as effective as higher doses in active early RA ([ter Wee et al, 2015](#)). A two weeks duration of therapy was chosen on the basis that prior study has suggested that this duration can significantly impact disease activity as measured by DAS28 score ([Gerlag et al, 2004](#)).

A dose AZD9567 of 40 mg has been selected based on review of available safety, PK, and PD data from the first studies in humans in which AZD9567 was administered to healthy volunteers as single doses 2, 10, 20, 40, 80, 100, 125 and 155 mg (D6470C00001) and, in a multiple dose setting, once daily for 5 days using 10, 20, 40 and 80 mg. (D6470C00002). AZD9567 was well tolerated in all studied dose levels.

The selected AZD9567 dose 40 mg showed effects on inflammatory activity (reduced lipopolysaccharide (LPS) stimulated TNF_α response) and on the HPA axis (plasma cortisol reduction) similar to what was observed for 20 mg prednisolone.

Although the selected comparator dose of 20 mg prednisolone is known to be efficacious in RA and considered safe and tolerable for 14 days administration, it also has significant effect on glucose homeostasis. The 40 mg dose of AZD9567 showed a significantly better side effect profile with respect to glucose levels after an oral glucose tolerance test (OGTT) compared to prednisolone 20 mg in the ongoing MAD study (D6470C00002).

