4. STUDY PLAN AND TIMING OF PROCEDURES

Table 1 Study Plan detailing the procedures

Study procedures	Screening Visit 1	Day 1 Visit 2 (within 1 week of V1)	Day 5 Phone call Visit 3	Day 8 +/- 1 Visit 4	Day 15 +/- 1 EOT ^a Visit 5	Day 28 +/- 2 Follow-up Visit 6
Inclusion/exclusion criteria	X					
Demographic data	X					
Medical history (incl. RA history and oral health)	X					
Concomitant medication	X	X	X	X	X	X
Informed consent	X					
Informed consent for genetic sample	X					
Randomisation		X				
Study drug dispensation		X ^b		X		
Study drug administration:		X ^b	→	→ NB: at site	X NB: at site	
Study drug return					X	
Adverse events		X	→	→	→	X
Serious adverse events	X	→	→	→	→	X
Vital signs (BP/P and body temperature)	X	X ^d		X	X	X
12-lead ECG	X	X ^{d, f}			X	X
Clinical laboratory evaluations (Haematology, serum biochemistry, endocrinology ^e , and urine ^e analysis)	X ^c	X ^d		X ^d	X ^d	X
Pregnancy test (serum)	X					X
Erythrocyte sedimentation rate, ESR (at site)	X	X ^d		X ^d	X ^d	X
Physical examination,	X	X		X	X	X
Body weight & height ^e	X				X	X
DAS28-CRP	X	X ^d		X	X	X
ACR20, 50, and 70	X	X ^d		X	X	X
SJC and TJC 66/68	X	X ^d		X	X	X
Blood sampling for exploratory biomarkers (cortisol, serum)		X ^{d,g} Profile: 0, 1, 2, 3, 4 and 6 h			Pre dose ^g & 1, 2, 3, 4 and 6 h post dose	
Blood sampling for exploratory biomarkers (LPS stimulated TNF α , whole blood)		X ^d Profile: 0, 1, 2, 3, 4 and 6 h			Pre dose & 1, 2, 3, 4 and 6 h post dose	
Blood sample (whole blood) for mRNA ⁱ		X ^d			X ^h	

Table 1 Study Plan detailing the procedures

Study procedures	Screening Visit 1	Day 1 Visit 2 (within 1 week of V1)	Day 5 Phone call Visit 3	Day 8 +/- 1 Visit 4	Day 15 +/- 1 EOT ^a Visit 5	Day 28 +/- 2 Follow-up Visit 6
Blood sample for other potential biomarkers (serum)		X ^d			X ^d	X
Blood sample for DNA (future exploratory research)		X ^b				
Blood sampling for PK of AZD9567/ prednisolone					Pre-dose, 0.25, 0.5, 1, 1.5, 2, 3, 4 and 6 h	

^a End of treatment

^b After randomisation

^c Local lab

^d Pre-dose

^e Only at Visit 1

^f Only performed if Visit 1 was >3 days ago

^g Preferably starting as close to 08.00 as possible

^h At 1h post dose (C_{max})

ⁱ A peripheral blood mononuclear cell method may be used at selective site/s

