3.5 Exploratory outcomes

3.5.1 Biomarkers

Whole blood and serum/plasma will be collected to enable relevant analyses such as, effects on bone, metabolism and HPA axis by assessment of:

- Individual LPS-stimulated WB TNF α levels (pg/mL).
- Individual plasma cortisol (nmol/L) AUEC $_{(0-6)}$.
- Change from baseline for morning plasma cortisol (nmol/L) at Day 15 and follow-up visit.

For each subject, the total AUEC at Day 1 and Day 15 will be calculated for plasma cortisol. Plasma cortisol is collected pre-dose only on Day 1 at 0, 1, 2, 3, 4 and 6 hours, and then pre-dose and post-dose at 1, 2, 3, 4 and 6 hours on Day 15. Each AUEC will be calculated using trapezoids as

$$AUEC = \sum_{i=1}^6 (t_{i+1} - t_i) \frac{y_{t_{i+1}} + y_{t_i}}{2}$$

The summation is over all available time points. The y_t are the concentration measurements. If any two consecutive measurements are missing, or if one or both of the measurements at time 0 for Day 1, pre-dose for Day 15 or 6 hours on either day are missing, then the AUEC for that day is missing. However, if the measurement at any single intermediate number of hours is missing, the AUEC will be calculated using linear interpolation.

For example, if measurements are available at only 0, 1, 2, 3 and 6 hours for Day 1, then

$$AUEC = (1 - 0) \frac{y_1 + y_0}{2} + (2 - 1) \frac{y_2 + y_1}{2} + (3 - 2) \frac{y_3 + y_2}{2} + (6 - 3) \frac{y_6 + y_3}{2}$$

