4.3.3.2 Plasma cortisol (nmol/L) AUEC(0-6) biomarkers

Individual plasma cortisol (nmol/L), will be listed and summarised by treatment, study day and time point using descriptive statistics (n, arithmetic mean, SD, geometric mean, geometric SD, geometric CV%, minimum, median, and maximum).

Arithmetic mean (+/- SE bars) plasma cortisol (nmol/L) versus time will be plotted by study day and treatment. A panel plot will be used with Day 1 and Day 15 displayed side-by-side. AUEC(0-6) plasma cortisol will be analysed on the log scale for change from baseline (defined as the Day 1 measurements) to Day 15. Therefore, the change from baseline in AUEC(0-6) plasma cortisol, when back-transformed from the log scale, will be a relative change from baseline (ratio).

$$\frac{\text{Day 15 AUEC}(0-6)}{\text{Day 1 AUEC}(0-6)}$$

The relative change from baseline in AUEC(0-6) plasma cortisol (nmol/L) will be analysed as follows:

- The change from baseline to Day 15 in the log-transformed AUEC(0-6) plasma cortisol will be analysed using ANCOVA model with log plasma cortisol AUEC(0-6) at baseline as covariate and treatment group as factor.

Where:

Log transformed AUEC(0-6) = Change from baseline in the log-transformed AUEC(0-6) plasma cortisol, i.e. $\log(\text{AUEC}(0-6) \text{ at Day 15}) - \log(\text{AUEC}(0-6) \text{ at Day 1})$

- The back-transformed LS-Means and 95% confidence interval will be presented by treatment group to present relative change from baseline to Day 15 (ratio). The difference relative to prednisolone 20mg (ratio) will be presented along with 95% confidence interval and p-value for two-sided comparison.

LS-Means for each treatment group, LS-mean difference between treatment groups and corresponding confidence interval limits will be back-transformed from the log scale by exponentiating.

A figure will be provided displaying the LSM relative change from baseline to Day 15 in plasma cortisol AUEC(0-6) by treatment group, along with the 95% CI. Individual values will be overlaid on the same figure as scatter points. The treatment groups will be presented side-by-side on the x-axis.

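### LPS-stimulated TNFα is profiled in every patient on Day 1, but the SAP plans no estimate that uses that profile as the patient's own baseline

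*SAP*

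**What the plan says.** **TNFα analysis.** In SAP 4.3.3.1 the levels in pg/mL "will be listed and summarised by treatment, study day and time point using descriptive statistics", and those statistics include geometric mean, geometric SD and geometric CV. Arithmetic means with standard-error bars are plotted over time: "A panel plot will be used with Day 1 and Day 15 displayed side-by-side". A further graph shows individual TNFα "following AZD9567 treatment versus individual AZD9567 levels (nmol/L) from the same sampling time points will be made". SAP 3.5.1 likewise names only individual TNFα levels as the variable. Neither section plans a change from Day 1, an AUEC, a model, or a between-arm estimate with an interval.

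**TNFα sampling.** Protocol Section 4, Table 1, has a Day 1 entry for whole-blood TNFα, footnoted as pre-dose, of "Profile: 0, 1, 2, 3, 4 and 6 h". The Day 15 entry is "Pre dose & 1, 2, 3, 4 and 6 h post dose". The two days share one time grid. PK is sampled on Day 15 only, at times that include all six TNFα times.

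**Cortisol.** Table 1 gives it the same schedule, and SAP 3.5.1 states that "Plasma cortisol is collected pre-dose only on Day 1 at 0, 1, 2, 3, 4 and 6 hours". SAP 4.3.3.2 then analyses the log Day 15/Day 1 ratio of AUEC(0-6) with an "ANCOVA model with log plasma cortisol AUEC(0-6) at baseline as covariate and treatment group as factor", and reports a ratio to prednisolone with a 95% CI.

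**Link to the dose.** Protocol 1.2 supports 40 mg partly by its effect on LPS-stimulated TNFα and "on the HPA axis (plasma cortisol reduction) similar to what was observed for 20 mg prednisolone". It also cites safety, PK and glucose findings.

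**The concern.** The stated exploratory objective (Protocol 2.4, SAP 1.1.4) is to assess how biomarkers respond to AZD9567, and TNFα is the first one listed. A patient's response is a departure from that patient's own untreated level. Table 1 supplies such a level, but no planned summary or figure uses it patient by patient.

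Two displays are affected. The group panels compare Day 1 with Day 15 as if they were separate samples. The concentration graph holds only Day 15 data, because there is no Day 1 PK, so a patient with habitually high TNFα release looks like a poor responder at any concentration.

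The SAP treats cortisol differently and gives no reason. TNFα is the anti-inflammatory marker of the two, so the trial would estimate the AZD9567/prednisolone ratio in patients for HPA-axis suppression but not for the TNFα effect. What is at stake is the precision of an exploratory readout, not the trial's main conclusion.

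**Working it through.** The documents state no TNFα SD, CV, correlation or effect size, so there is no plan figure to reproduce. CV, correlation and true reduction below are assumptions, shown over ranges.

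**Inputs.** n = 10 per arm (SAP 1.3; SAP Section 6 records the reduction from 18). Assumed between-patient CV: 50% and 80%. Assumed Day 1 to Day 15 correlation on the log scale, ρ: 0.5 to 0.9.

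**1. Between-arm ratio.** Log-scale SD is s = √ln(1 + CV²):
- CV 50%: s = √ln 1.25 = 0.472
- CV 80%: s = √ln 1.64 = 0.703

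The 95% CI is the estimate multiplied and divided by a factor:
- Day 15 values alone: exp(t₁₈ · s · √(2/10)), with t₁₈ = 2.101
- ANCOVA on Day 1: exp(t₁₇ · s · √(1 − ρ²) · √(2/10)), with t₁₇ = 2.110

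Worked case, CV 80%: 0.703 × 0.447 = 0.3145. Day 15 alone gives exp(2.101 × 0.3145) = 1.94. With ρ = 0.7, √(1 − 0.49) = 0.714, and exp(2.110 × 0.3145 × 0.714) = 1.61.

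| CV | Day 15 alone | ANCOVA, ρ = 0.5 | ρ = 0.7 | ρ = 0.9 |
|---|---|---|---|---|
| 50% | 1.56 | 1.47 | 1.37 | 1.21 |
| 80% | 1.94 | 1.78 | 1.61 | 1.34 |

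The equivalent sample size without adjustment is 10/(1 − ρ²) per arm: 13.3 at ρ = 0.5 and 19.6 at ρ = 0.7.

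**2. Form of the adjustment.** A plain log change without the covariate replaces √(1 − ρ²) by √(2(1 − ρ)). At CV 80% its factor is 1.94 for ρ = 0.5, no better than Day 15 alone, and 2.19 for ρ = 0.3, which is worse. ANCOVA at ρ = 0.3 gives 1.88. The covariate is therefore needed.

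**3. When unpaired data suffice.** Normal-approximation power to see a fall from Day 1 to Day 15 within one arm, Φ(d/SE − 1.96), with d = −ln(1 − reduction) and SE = s√(2/10):

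| True fall | CV 30% | CV 50% | CV 80% | CV 120% |
|---|---|---|---|---|
| 30% | 78% | 39% | 20% | 13% |
| 50% | about 100% | 91% | 60% | 38% |
| 70% | about 100% | about 100% | 97% | 81% |

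Pairing multiplies SE by √(1 − ρ). For a 50% fall at CV 80%, 60% becomes 88% (ρ = 0.5) or 98% (ρ = 0.7). The approximation is somewhat generous at n = 10, but the contrast stands.

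**4. Concentration plot.** A simulation of 10 patients at 6 times assumed a maximum inhibition of 50% or 80%, CV of 50% or 80%, and ρ of 0.5 or 0.8. Subtracting the patient's log-scale Day 1 mean strengthened the correlation with concentration in all eight settings. The median went from −0.16 to −0.31 at inhibition 50%, CV 80%, ρ 0.8, and from −0.46 to −0.70 at inhibition 80%, CV 50%, ρ 0.8.

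The denominator matters. If sample errors are independent, the noise variance is s² for raw levels, 2(1 − ρ)s² for a ratio to one time-matched Day 1 sample, and (1 − ρ)(1 + 1/6)s² for a ratio to the mean of six. At ρ = 0.3 these are 1.00, 1.40 and 0.82 times s². A single-sample denominator can therefore add noise.

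**The case against.** The strongest case against is that nothing here is an error. TNFα is exploratory and reported outside the CSR (SAP 1.1.4), SAP 3.5.1 and 4.3.3.1 agree with each other, and Protocol 8.5.5 leaves room for further exploratory analyses. The planned output is also not bare. Geometric statistics, every individual value and side-by-side Day 1 panels are provided, which give an unpaired group reference in both arms and keep the paired data visible. The SAP plans no between-arm TNFα interval, so the factor of 1.94 is a benchmark brought in by this check. Clinical comparison with prednisolone rests on DAS28-CRP and its components, which do get baseline-adjusted models.

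All of that stands, and it limits the priority. It does not explain why cortisol, equally exploratory and on the same schedule, gets a baseline-adjusted estimate and TNFα does not. Separate reporting is no explanation either, since SAP 1.1.4 makes this SAP the place where the TNFα analyses are set out.

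A reader might infer three stronger things that the documents do not support:
- **That patient spread swamps the drug effect.** This needs a variance and an effect size that are not given. Step 3 shows that a 70% fall would be seen with at least 81% power even unpaired, while a 30% fall at CV 80% would usually be missed.
- **That the planned summaries cannot show any response.** They can, at group level.
- **That the 40 mg dose rests on TNFα.** Protocol 1.2 lists it among several grounds, from healthy volunteers.

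**Conclusion.** The point holds as a missed, nearly free gain in precision. SAP 4.3.3.1 plans no estimate that links Day 15 TNFα to the patient's own Day 1 profile, although the profile is collected and the method is already written for cortisol. Between-patient spread may obscure the TNFα response and its comparison with prednisolone 20 mg; whether it will cannot be told from the documents.

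At 10 per arm, the gain in the between-arm CI factor runs from slight (1.56 to 1.47 at CV 50%, ρ 0.5) to large (1.94 to 1.34 at CV 80%, ρ 0.9). These figures rest on assumed CVs and correlations, log-normal data and complete profiles in all 20 patients. They also take the Day 1 TNFα profile as untreated, which comes from the Table 1 footnote; the SAP's explicit statement to that effect is about cortisol.

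**What to change.** In SAP 4.3.3.1:

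1. Derive TNFα AUEC(0-6) on Day 1 and Day 15 by the trapezoid and missing-value rule of SAP 3.5.1, and confirm there that the Day 1 TNFα profile is pre-dose.
2. Analyse log(Day 15) − log(Day 1) with the SAP 4.3.3.2 ANCOVA: log Day 1 AUEC as covariate, treatment as factor.
3. Report the Day 15/Day 1 ratio per arm and the AZD9567/prednisolone ratio, each with a 95% CI, labelled exploratory.
4. Keep the planned concentration graph and add a version with TNFα relative to the patient's own Day 1 mean. A mean is preferable to a single time-matched sample because it is less noisy, though it does not remove any time-of-day trend.

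The existing descriptive tables, listings and panels can stay as they are. The cost is reuse of the cortisol program on samples already scheduled, with no extra blood or assays. The downsides are one more exploratory interval, and the loss from the model of patients whose AUEC is missing on either day; their values remain in the listings.

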4.3.3.2 Plasma cortisol (nmol/L) AUEC(0-6) biomarkers

Individual plasma cortisol (nmol/L), will be listed and summarised by treatment, study day and time point using descriptive statistics (n, arithmetic mean, SD, geometric mean, geometric SD, geometric CV%, minimum, median, and maximum).

Arithmetic mean (+/- SE bars) plasma cortisol (nmol/L) versus time will be plotted by study day and treatment. A panel plot will be used with Day 1 and Day 15 displayed side-by-side. AUEC(0-6) plasma cortisol will be analysed on the log scale for change from baseline (defined as the Day 1 measurements) to Day 15. Therefore, the change from baseline in AUEC(0-6) plasma cortisol, when back-transformed from the log scale, will be a relative change from baseline (ratio).

$$\frac{\text{Day 15 AUEC}(0-6)}{\text{Day 1 AUEC}(0-6)}$$

The relative change from baseline in AUEC(0-6) plasma cortisol (nmol/L) will be analysed as follows:

- The change from baseline to Day 15 in the log-transformed AUEC(0-6) plasma cortisol will be analysed using ANCOVA model with log plasma cortisol AUEC(0-6) at baseline as covariate and treatment group as factor.

Where:

Log transformed AUEC(0-6) = Change from baseline in the log-transformed AUEC(0-6) plasma cortisol, i.e. $\log(\text{AUEC}(0-6) \text{ at Day 15}) - \log(\text{AUEC}(0-6) \text{ at Day 1})$

- The back-transformed LS-Means and 95% confidence interval will be presented by treatment group to present relative change from baseline to Day 15 (ratio). The difference relative to prednisolone 20mg (ratio) will be presented along with 95% confidence interval and p-value for two-sided comparison.

LS-Means for each treatment group, LS-mean difference between treatment groups and corresponding confidence interval limits will be back-transformed from the log scale by exponentiating.

A figure will be provided displaying the LSM relative change from baseline to Day 15 in plasma cortisol AUEC(0-6) by treatment group, along with the 95% CI. Individual values will be overlaid on the same figure as scatter points. The treatment groups will be presented side-by-side on the x-axis.

4.3.3.3 Morning plasma cortisol (nmol/L) biomarkers

Morning plasma cortisol includes 2 measurements per subject, i.e. first pre-dose measurement (08:00am) at baseline and pre-dose at Day 15.

Change from baseline in morning plasma cortisol (nmol/L) will be analysed using an ANCOVA model with covariate baseline morning plasma cortisol (nmol/L) and treatment group as a factor. LS-Means and 95% confidence interval for the change from baseline in morning plasma cortisol (nmol/L) at Day 15 will be presented by treatment group. P-value for the two-sided comparison

to baseline will be provided for each treatment group. For this variable no comparison to prednisolone 20mg will be done.

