NB. In case a subject shows an AST **or** ALT $\geq 3 \times \text{ULN}$ **or** total bilirubin $\geq 2 \times \text{ULN}$ please refer to [Appendix D](#) ‘Actions required in cases of combined increase of Aminotransferase and Total Bilirubin - Hy’s Law’, for further instructions.

Table 3 Volume of blood to be drawn from each patient

Assessment	No of samples ^b	Sample volume (mL)	Total volume (mL) ^b
Safety - Clinical Chemistry	5	5	25
Safety - Haematology	5	2	10
Endocrinology (FSH) ^a	1	2.5	2.5
Exploratory Biomarkers (whole blood mRNA)	2	5	10
Other Potential Biomarkers (serum)	3	2 x 8.5	2 x 25.5
Exploratory Biomarkers (whole blood for TNF α)	12	2	24
Exploratory Biomarkers (serum for cortisol)	12	8	96
PK samples for AZD9567/prednisolone	9	3	27
Pharmacogenetics	1	10	10
TOTAL	53		255.5

^a only females

^b The number of samples may be changed due to additional sampling at unscheduled visits and the blood volume required may be altered to fit the assay requirements.

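### The SAP withholds the randomised comparison for morning cortisol that its own ANCOVA estimates, and lists a follow-up cortisol value with no assigned sample

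*SAP*

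**What the plan says.** **Model and reporting.** SAP 4.3.3.3 analyses change in morning cortisol with an "ANCOVA model with covariate baseline morning plasma cortisol (nmol/L) and treatment group as a factor". For each arm it presents the LS-mean with a 95% CI at Day 15. A "P-value for the two-sided comparison" to baseline is given separately for each arm. The section ends: "For this variable no comparison to prednisolone 20mg will be done".

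**The neighbouring section.** SAP 4.3.3.2 fits an ANCOVA of the same form to log cortisol AUEC(0-6). There it presents the ratio to prednisolone with a 95% CI and a two-sided p-value.

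**Measurements.** SAP 3.5.1 lists the outcome as "Change from baseline for morning plasma cortisol (nmol/L) at Day 15 and follow-up visit". SAP 4.3.3.3 says: "Morning plasma cortisol includes 2 measurements per subject, i.e. first pre-dose measurement (08:00am) at baseline and pre-dose at Day 15". In the protocol's study plan (section 4, Table 1), the row "Blood sampling for exploratory biomarkers (cortisol, serum") has entries at Visits 2 and 5 only. The blood-volume table (protocol 5.2.1, Table 3) counts 12 samples of 8 mL in the row "Exploratory Biomarkers (serum for cortisol").

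**The concern.** The treatment coefficient in this ANCOVA is the baseline-adjusted difference between the randomised arms. The plan estimates it and does not report it. What it prints is one test against baseline per arm. A reader with two such p-values will tend to compare them, and that goes wrong in both directions: one significant and one non-significant result can arise from identical effects, and two significant results can hide a real difference. A within-arm change also absorbs anything that shifts between Day 1 and Day 15, such as clock time of sampling, which Table 1 of the protocol states only as a preference. The randomised difference protects against such shifts.

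AUEC(0-6) is not a full substitute. Five of its six Day 15 points are post-dose, so it includes the response to that day's dose, while morning cortisol is the pre-dose value. Plasma cortisol is also the one exploratory biomarker that SAP 1.1.4 sends to the CSR.

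The follow-up value is a separate matter: an outcome is listed that the analysis section does not analyse and for which no cortisol sample is scheduled.

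**Working it through.** **1. Sample count (protocol Tables 1 and 3).** Cortisol is drawn at 0, 1, 2, 3, 4 and 6 h at Visit 2 and at the matching six points at Visit 5.
- Samples: 6 + 6 = 12. Volume: 12 × 8 mL = 96 mL. Both match Table 3.
- The table totals also reproduce if the other biomarker serum is counted as 3 × 2 = 6 tubes: 5 + 5 + 1 + 2 + 6 + 12 + 12 + 9 + 1 = 53 samples, and 25 + 10 + 2.5 + 10 + 51 + 24 + 96 + 27 + 10 = 255.5 mL.
- The 12 cortisol samples are used up by Visits 2 and 5. One more at Visit 6 would make the cortisol row 13 samples and 104 mL, and the totals 54 and 263.5 mL.

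**2. What within-arm p-values say about the arms.** Inputs:
- n = 10 per arm (SAP 1.3).
- Two-sided 5% (SAP 4.3.1, stated under the primary model and taken here as the default).
- Model: change on baseline plus treatment, residual df = 2 × 10 − 3 = 17.
- The documents give no cortisol SD or expected change, so the true change is an assumption, varied from 0 to 1.5 residual SD.

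With s² the residual variance, x̄ the baseline means and Sxx the pooled within-arm sum of squares of baseline:
- Within-arm test: LS-mean / SE, with SE² = s²[1/n + (x̄_arm − x̄)²/Sxx].
- Between-arm test: difference in LS-means / SE, with SE² = s²[2/n + (x̄_A − x̄_P)²/Sxx].

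Simulated with 20,000 trials per row and the same true change in both arms:

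| True change (residual SD) | One arm significant, the other not | Between-arm test significant |
|---|---|---|
| 0 | 9.5% | 5.1% |
| 0.3 | 24% | 5.2% |
| 0.6 | 46% | 4.8% |
| 0.7 | 47% | 5.0% |
| 1.0 | 27% | 5.1% |
| 1.5 | 1.4% | 4.9% |

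A repeat with 200,000 trials per row agreed to within one percentage point and gave 1.6% in the last row, hence about 2% at the low end.

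Cross-check: for two independent tests with power p, the chance of disagreement is 2p(1 − p), which peaks at 2 × 0.5 × 0.5 = 50%. The simulated peak is slightly lower because both tests share one residual variance.

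**3. The opposite error.** With true changes of 1.5 and 2.5 residual SD, which differ by 1 SD, both within-arm tests are significant in 99% of trials. The pair of p-values then shows no contrast. The between-arm test detects the difference in 53%.

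**The case against.** The strongest defence has four parts.

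- **Cortisol is still compared with prednisolone.** SAP 4.3.3.2 does so for AUEC(0-6), and the Day 15 pre-dose value is the first point of that profile. This stands. A reader might infer that the HPA-axis comparison is lost altogether, and the documents do not support that.
- **The biomarker objective names no comparator.** Protocol 2.4 and SAP 1.1.4 speak of responses to AZD9567. Similarity to prednisolone appears in protocol 1.2 as dose-selection evidence. This also stands: a within-arm change does address the objective as worded, so the arm-level estimates should stay. It is no reason to withhold the contrast.
- **The loss is small.** Each arm's LS-mean and CI come from one model, so the point difference is a subtraction. The modelling is exploratory (SAP 4.3.2), and SAP 1.3 says the trial is not powered for testing. True, but the CI of the difference is what conveys the uncertainty, and it is not printed. Low power favours an estimate with a CI over two p-values.
- **Disagreement may be rare.** If both drugs suppress cortisol clearly, it falls to about 2%. That stands, and it is why the range must include its low end. In that situation, however, the pair of p-values also cannot reveal a real difference (step 3).

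On follow-up, a reader might infer that the value cannot be produced at all. That goes too far. The row "Blood sample for other potential biomarkers (serum") includes a Visit 6 draw that no section assigns to cortisol, and a footnote to Table 3 lets sample numbers change. What is established is that no sample is assigned to cortisol at that visit.

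**Conclusion.** The point holds as a minor one on an exploratory outcome. For morning cortisol, the plan omits the randomised contrast that its own model yields, and it gives no reason for treating this outcome differently from AUEC(0-6). At n = 10 per arm with equal true changes, the within-arm tests disagree in about 2% to 47% of trials, while the between-arm test stays near 5%. The range depends on an assumed true change of 0 to 1.5 residual SD, a common residual variance and normal errors. Nothing in the documents places the trial at any one point in the range, so quoting only its upper part would not be justified.

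The follow-up entry is a conflict between SAP 3.5.1 on one side and SAP 4.3.3.3 and protocol Tables 1 and 3 on the other. It stands whatever is decided about the contrast.

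**What to change.** 1. In SAP 4.3.3.3, replace the sentence excluding the comparison with a statement that the AZD9567 minus prednisolone LS-mean difference at Day 15 will be reported with its 95% CI, from the ANCOVA already planned. Keep each arm's LS-mean and 95% CI. If the within-arm p-values stay, state that they are not used to compare arms. Cost: one extra estimate from an existing model, with no new data.
2. Reconcile SAP 3.5.1 with SAP 4.3.3.3 and protocol Tables 1 and 3. Either delete the follow-up visit from the outcome, or name the Visit 6 sample, its time of day and its matrix (the protocol says serum, the SAP plasma), and add the analysis. Deletion costs an edit. Naming a sample costs about one assay per patient, and depends on whether the unassigned Visit 6 serum may be used for cortisol and was drawn in the morning, which the available text does not settle.
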